## Statistical Analysis Plan (SAP)

---

### 6 Sample Size and Power

This phase 2 trial is not powered to conduct formal hypothesis testing. The target enrollment of 375 subjects for Cohorts 1-3 and 250 subjects for Cohort 4 were based on previous experiences from studies conducted with similar products.

## Statistical Analysis Plan (SAP)

---

### 7 Analysis Populations

#### 7.1 Description of Analysis Populations

##### 7.1.1 Intention-to-Treat (ITT) Population

The ITT population includes all subjects who are randomized. Subjects in this population will be analyzed according to their randomized treatment assignment.

##### 7.1.2 Safety Population

The Safety population includes all subjects in the ITT population who receive at least one dose of IP. Subjects in this population will be analyzed according to the actual treatment received.

##### 7.1.3 Per-Protocol (PP) Population

The PP population includes all ITT subjects who received all planned treatments and have no major/key excluding protocol deviations. Subjects in this population will be analyzed according to their randomized treatment assignment. Subjects excluded from the PP population will be identified and documented prior to unblinding of the trial database; however, the PP population will not be used for any TFL summaries. All TFL summaries will be presented among one or more of the ITT, Safety, PK, and/or PD populations.

##### 7.1.4 Pharmacodynamic (PD) and Pharmacokinetic (PK) Populations

The PK and PD populations include all Safety population subjects who have sufficient evaluable PK or PD samples, respectively. The evaluable PK or PD samples should be able to provide reliable estimation of PK or PD parameters for at least one of the mABs or serotypes BoNT/A or BoNT/B. Subjects in these samples will be analyzed according to the actual treatment received.

#### 7.2 Protocol Deviations/Violations and Exclusions from Analysis Sets

Protocol deviation data will be captured in the clinical trial management system. Extracts of all protocol deviations will be reviewed periodically and prior to final analysis. All protocol deviations and the exclusion of participants from analysis sets will be identified prior to unblinding, through clinical review input provided by Resilience Government Services, Inc. using supportive participant listings, provided by the ICON biostatistician based upon data recorded in the clinical trial management system.

Further, deviations from the protocol will be classified as major/key or minor/non-key. Classification of major and minor protocol deviations is determined prior to participant enrollment and is outlined in detail in the protocol deviation criteria documentation managed by the clinical trial management team.

### 8 Statistical Considerations and Analysis

#### 8.1 Derived Variables

The below table provides the list of derived variables for demographic and baseline characteristics, various duration derivations, baseline derivation and other important derivations applicable for this segment of the trial.

**Table 3: Derived Variables**

Variable	Formula
Demographic and Baseline Characteristics	
Body Mass Index	weight (kg) / [height (m)] 
Age	Calculated at the time of informed consent. Sample SAS code to calculate age is: age = floor((informed consent date - date of birth)/365.25)
Baseline	Baseline is defined as the last measurement prior to the first treatment administration
Derivation of Durations	
Study day at any visit	date of visit – date of first dose. One day is added if the difference is ≥ 0.
Duration of any events	end date of event – start date of event + 1
Other Derivations	
Incidence in a group	The proportion of the participants experiencing the outcome of interest compared to the total number of participants at risk of experiencing the outcome of interest. (e.g., the incident rate of SAEs after injection are the number of participants with an SAE reported after injection divided by the number of participants that received the injection).
Pharmacodynamic (PD) Parameters	
AUC (0-t)	Area under the concentration time-curve from the time of dosing to the time of the last measurable (positive) concentration
C max	Maximum observed concentration, occurring at time T max .
T max	Time of maximum observed concentration. For non-steady-state data, the entire curve is considered. If the maximum observed concentration is not unique, then the first maximum is used.
t 1/2	Terminal half-life defined as ln(2)/ λ z as measured during steady-state
Pharmacokinetic (PK) Parameters	

## Statistical Analysis Plan (SAP)

Variable	Formula
Kel	First-order rate constant associated with the terminal (log-linear) portion of the curve, estimated by linear regression of time vs. log concentration during steady-state elimination
AUC (0-t)	Area under the concentration time-curve from the time of dosing to the time of the last measurable (positive) concentration
AUC (0-∞)	Area under the concentration time-curve from time of dosing extrapolated to infinity, based on the last observed concentration or last predicted concentration defined as AUC (0-t) + (C (0-t) /λ z )
t 1/2	Terminal half-life defined as ln(2)/ λ z as measured during steady-state
CL/F	Total body clearance for extravascular administration defined as Dose/ AUC (0-∞)
V z /F	Volume of distribution based on the terminal phase. For non-steady-state data defined as Dose/[ λ z (AUC (0-∞) )]

### 8.2 Missing Data Analysis Methods

### 8.3 Handling of Missing Data and Outliers

All attempts will be made to collect data as prescribed by the clinical protocol. No imputations will be conducted for missing data except for the following scenarios:

- BLQ (Below Limit of Quantitation) results for PD and PK analyses: BLQ values will be treated as zero prior to the first measurable concentration. After the first measurable concentration, subsequent BLQ values will be treated as missing. In the calculation of geometric means and coefficients of variation, 0.001 will be imputed for zero values.
- Titer results below detectable threshold for ADA analysis: Titer values presented as inequalities due to being below the detectable threshold will be reported as their numeric value without the inequality qualifier
- Laboratory results below detectable threshold for laboratory analysis: Laboratory results presented as inequalities (or which otherwise have a non-numeric qualifier) will be presented as the numeric value without its non-numeric qualifier

Outliers identified in the PK analyses will be discussed in the analysis report.

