### 2 Study Objectives

#### 2.1 Primary Objectives

- To evaluate the safety and tolerability of single or repeat intramuscular (IM) administration of G03-52-01 in healthy adult subjects
- For Cohorts 1-3 (Cohorts 1-2 active IP and Cohort 3 is placebo)
  - Demonstrate target protective concentration (NAC) value  $> 0.02$  U/mL (BoNT/A) or  $> 0.03$  U/mL (BoNT/B) at Day 45 and Day 90
  - To evaluate lot-to-lot variability of two doses of G03-52-01 (Note: There will be no formal statistical analysis to support evaluation of lot-to-lot variability. In table summaries, the two lots within each of Cohorts 1 and 2 will be summarized and displayed separately to visually assess lot-to-lot variability.)
- For Cohort 4 (only active IP), demonstrate target protective concentration (NAC) value of BoNT/A and BoNT/B at 4 and 8 hours post-dose

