Vital sign assessments will be performed at all in-clinic study visits, including systolic and diastolic blood pressure (BP), heart rate (HR), and oral temperature. During screening and follow-up, a measurement that is a Grade 1 (as referenced in Protocol G03-52-01-002, v4.0, 14Apr2024, Appendix B) may be repeated once if the principal investigator believes a transient condition led to the aberrant value. Vital signs obtained at screening will serve as baseline values for the subject. Grade 1 values are allowable unless deemed clinically significant by the study Investigator.

- **Electrocardiogram (ECG)**

A 12-lead ECG will be performed at screening and reviewed by the study PI or a co-Investigator to assess the cardiac status of a subject for eligibility for enrollment.

- **Laboratory Evaluations**

Laboratory assessment schedule will follow the Schedule of Assessments in Appendix A. Detailed laboratory tests can be found in Section 8.5.2 of Protocol G03-52-01-002, v4.0, 14Apr2024.

- **Pharmacodynamic (PD) and Pharmacokinetic (PK) Assays**

Blood samples for PD assessment will be collected at pre-dose, 24 hours post-dose, and on Days 8, 15, 45 (prior to dosing) 49, 90, and 120 for all subjects in Cohorts 1-3. The first 25 subjects randomized for each DP lot of 50 mg and 100 mg doses and placebo will be tested at all 8 timepoints. The remaining samples from the subjects who received either dose or lot of G03-52-01 (including placebo) will only be tested using MNA at pre-dose and Days 45, 90, and 120.

Blood samples for PD assessment will be collected at pre-dose, 2 hours, 4 hours, 8 hours, 24 hours, and on Days 30, 45, and 90 for all subjects in Cohort 4. Cohort 4 samples for the first 30 subjects, who receive active drug product and complete sample collection at 24 hours, will be tested at pre-dose, 2 hours, 4 hours, 8 hours, 24 hours, and on Days 30, 45, and 90. PD samples will be analyzed for neutralizing antibody concentration (NAC) using the validated Battelle MNA.

Blood samples for PK assessment will be collected at pre-dose, 24 hours and 72 hours post-dose, and on Days 8, 15, 45 (prior to dosing), 49, 90, and 120 for all subjects in Cohorts 1-3. The first 25 subjects randomized for each DP lot of 50 mg and 100 mg doses and placebo will be tested at all timepoints.

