**Table 2: Study Objective, Endpoint, and Statistical Methodology Overview**

Primary Objectives	Primary Endpoints	Statistical Methodology
Primary Objective #1: To evaluate the safety and tolerability of repeat intramuscular (IM) administration of G03-52-01 in healthy adult subjects	Primary Endpoint #1a: The occurrence of adverse events (AEs) and serious adverse events (SAEs) following administration of G03-52-01 to the final visit	Incidence rate of the various AE categories, and the counts and percentages of subjects that experienced them
	Primary Endpoint #1b: The occurrence of changes from baseline in PE, vital signs, and clinical safety laboratory values following administration of G03-52-01 to the final follow-up visit	Descriptive statistics for the change/shift from baseline in laboratory (chemistry and hematology), vital signs (heart rate, blood pressure, respiratory rate, pulse oximetry, and body temperature), and physical examination measures
Primary Objective #2: For Cohorts 1-3 (Cohorts 1-2 active IP and Cohort 3 is placebo): 
 
Demonstrate target protective concentration (NAC) value > 0.02 U/mL (BoNT/A) or > 0.03 U/mL (BoNT/B) at Day 45 and Day 90
 
To evaluate lot-to-lot variability of two doses of G03-52-01
 
	Primary Endpoint #2: For Cohorts 1-3, to evaluate the proportion of subjects with target protective concentration (NAC) value > 0.02 U/mL (BoNT/A) or > 0.03 U/mL (BoNT/B) at Day 45 and Day 90 (Note: There will be no formal statistical analysis to support evaluation of lot-to-lot variability. In table summaries, the two lots within each of Cohorts 1 and 2 will be summarized and displayed separately to visually assess lot-to-lot variability.)	Protective NAC rate at Day 45 and Day 90, where protective NAC rate is defined as the proportion of subjects with NAC value > 0.02 U/mL against BoNT/A or NAC value > 0.03 U/mL against BoNT/B

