### 9.10.3 Primary Endpoint 2 – Target Protective NAC (Day 45 and Day 90), Cohorts 1-2

To evaluate primary objective #2, to demonstrate target protective concentration (NAC) value of BoNT/A and BoNT/B through Day 45 and Day 90 for Cohorts 1-2, primary endpoint #2 will be used:

For Cohorts 1-2, to evaluate target protective concentration (NAC) value  $> 0.02$  U/mL (BoNT/A) or  $> 0.03$  U/mL (BoNT/B) at Day 45 and Day 90

PD samples will be collected and analyzed by the Battelle MNA against serotypes BoNT/A and BoNT/B at Baseline/Dosing [Visit 2 (Day 1)] pre-dose, Visit 3 (24 Hours), Visit 5 (Day 8), Visit 6 (Day 15), Visit 7 (Day 45) pre-dose, Visit 8 (Day 49), Visit 10 (Day 90), and Visit 11 (Day 120).

At Visit 7 (Day 45) and Visit 10 (Day 90), the frequency and percentage of subjects with a NAC  $> 0.02$  U/mL against BoNT/A, a NAC  $> 0.03$  against BoNT/B, and those with either a NAC  $> 0.02$  U/mL against BoNT/A or a NAC  $> 0.03$  U/mL against BoNT/B will be presented. Percentages will be based on the total number of subjects at the respective time point with evaluable concentrations. Summaries will be presented for each lot separately within each of the two active drug cohorts.

The PD population will be used for the analysis of this primary endpoint.

### 9.10.4 Primary Endpoint 3 – Target Protective NAC (4 Hours and 8 Hours), Cohort 4

To evaluate primary objective #3, to demonstrate target protective concentration (NAC) value of BoNT/A and BoNT/B at 4 and 8 Hours post-dose for Cohort 4 (active only), primary endpoint #3 will be used.

At 4 Hours post-dose and 8 Hours post-dose, the frequency and percentage of subjects with a NAC  $> 0.02$  U/mL against BoNT/A, a NAC  $> 0.03$  against BoNT/B, and those with either a NAC  $> 0.02$  U/mL against BoNT/A or a NAC  $> 0.03$  U/mL against BoNT/B will be presented. Percentages will be based on the total number of subjects at the respective time point with evaluable concentrations. Summaries will be presented for each lot separately within each of the two active drug cohorts.

The PD population will be used for the analysis of this primary endpoint.

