### 9.10.6 Secondary Endpoint 2 – PD and ADA Evaluation, Cohorts 1-2

To evaluate secondary objective #2, to evaluate pharmacodynamic (PD) and anti-drug antibody (ADA) at pre-dose through the end of study (Cohorts 1-2), secondary endpoint #2 will be used.

The following PD parameter estimates for samples analyzed using the Battelle Mouse Neutralization Assay (MNA) method will be reported:

- $AUC_{(0-t)}$ : Area under the concentration time-curve to the last concentration above the lower limit of quantitation (reported in day\*U/mL)
- $C_{max}$ : Maximum observed concentration (reported in U/mL)
- $T_{max}$ : Time of maximum observed concentration (reported in days)
- $t_{1/2}$ : Terminal elimination half-life (reported in days)

PD parameters will be summarized by lot and active cohort using descriptive statistics against each serotype (BoNT/A and BoNT/B) separately. Parameters will be calculated and presented separately for Dose 1 and Dose 2 where applicable.

Additionally, NAC values will be summarized descriptively for each serotype separately at Baseline/Dosing [Visit 2 (Day 1)] pre-dose, Visit 3 (24 Hours), Visit 5 (Day 8), Visit 6 (Day 15), Visit 7 (Day 45) pre-dose, Visit 8 (Day 49), Visit 10 (Day 90), and Visit 11 (Day 120). Concentration-time profiles will be displayed graphically on linear and semi-log scales by serotype and active treatment group. One set of plots will include error bars (presented as SD) and one set will not include error bars.

The summary statistics used for all PD parameters and concentrations will include number of subjects (n), mean, SD, median, Q1, Q3, minimum, maximum, coefficient of variation (CV, presented in percentage, CV%), geometric mean (GM), the 95% CI of the GM, the geometric coefficient of variation (GCV, presented in percentage, GCV%), and the 95% CI of the GCV%.

The GM, 95% CI of GM, GCV%, and 95% CI of GCV% will be calculated using the following SAS® procedure:

```
proc ttest data=indata dist=lognormal;
```

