## Statistical Analysis Plan (SAP)

---

```
var x;  
ods select ConfLimits;  
run;
```

, where `indata` is the data set with PD parameters and `x` is a parameter.

Additionally, PD parameters and NAC values will be listed separately at the subject level.

The PD population will be used for all pharmacodynamic tables, listings, and figures.

Immunogenicity (ADA) samples will be tested at Baseline/Dosing [Visit 2 (Day 1)] pre-dose, Visit 3 (24 Hours) and Visit 4 (72 Hours) post-dose, and at Visit 5 (Day 8), Visit 6 (Day 15), Visit 7 (Day 45) pre-dose, Visit 8 (Day 49), Visit 10 (Day 90), Visit 11 (Day 120), Visit 12 (Day 150), Visit 13 (Day 180), and Visit 14 (Day 240).

The frequency and percentage of subjects with a positive immunogenicity response will be summarized by time point across the active treatment arms. Additionally, anti-drug antibody titers will be summarized using continuous descriptive statistics [number of subjects (n), mean, SD, median, Q1, Q3, minimum, maximum, CV%, GM, GCV%, and the 95% CI of the GCV] by time point. Both the categorical and continuous ADA table summaries will include a subgroup analysis for only those subjects that have a negative immunogenicity response at baseline. Anti-drug antibody status and titer values will be listed by subject and time point.

The ITT population will be used for all immunogenicity summaries.

### 9.10.7 Secondary Endpoint 3 – Target Protective NAC (2 Hours), Cohort 4

To evaluate secondary objective #3, demonstrate target protective concentration (NAC) value of BoNT/A and BoNT/B at 4 and 8 hours post-dose (Cohort 4), secondary endpoint #3 will be used.

To evaluate the proportion of subjects with target protective concentration (NAC) value > 0.02 U/mL (botulinum neurotoxin [BoNT]/A) or > 0.03 U/mL (BoNT/B) at 2 hours post dose

At the 4 Hour and 8 Hour post-dose time points, the frequency and percentage of subjects with a NAC > 0.02 U/mL against BoNT/A, a NAC > 0.03 against BoNT/B, and those with either a NAC > 0.02 U/mL against BoNT/A or a NAC > 0.03 U/mL against BoNT/B will be presented. Percentages will be based on the total number of subjects at the respective time point with evaluable concentrations.

The PD population will be used for the analysis of this secondary endpoint.

### 9.10.8 Secondary Endpoint 4 – PK Evaluation, Cohort 4

To evaluate secondary objective #4, to assess pharmacokinetics (PK) at pre-dose through end of study (Cohort 4), secondary endpoint #4 will be used.

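### The BLQ-as-missing rule in SAP 8.3, joined to an undefined evaluable-concentration denominator, can remove assayed BLQ results from the protective-NAC rates

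*SAP*

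**What the plan says.** SAP 8.3 gives one BLQ convention for PD and PK analyses. BLQ values before the first measurable concentration are set to zero, and for later ones: "After the first measurable concentration, subsequent BLQ values will be treated as missing". In the same section, ADA titers and laboratory results below the detectable threshold are kept as numeric values.

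SAP 9.10.3 (Days 45 and 90, primary) and 9.10.5 (Day 120, secondary) report three rates in the PD population: above target for BoNT/A, above target for BoNT/B, and above target for either. The denominator is set by this sentence: "Percentages will be based on the total number of subjects at the respective time point with evaluable concentrations". SAP 9.10.4 and 9.10.7 (Cohort 4) use the same wording. Table 2 gives the either-serotype version, "where protective NAC rate is defined as the proportion of subjects with NAC value" above 0.02 U/mL for BoNT/A or above 0.03 U/mL for BoNT/B.

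The only description of what counts as evaluable is in SAP 7.1.4, where it governs entry to the population: "The evaluable PK or PD samples should be able to provide reliable estimation of PK or PD parameters".

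Under SAP 3.4, the first 25 subjects per dose-lot group are assayed at all eight time points. Samples from the rest "will only be tested using MNA at pre-dose and Days 45, 90, and 120". For PD parameters, SAP 9.10.6 adds: "Parameters will be calculated and presented separately for Dose 1 and Dose 2 where applicable".

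**The concern.** The NAC rates are PD analyses, and nothing exempts them from the BLQ rule. A value that has been set to missing is not naturally an evaluable concentration. Read together, the sections remove a subject who was measurable earlier and is BLQ at the visit in question, although the sample was assayed and the result is informative. A subject who was never measurable is set to zero and counted as not protected. A quantified value at or below target also stays in as a failure. The results that drop out are therefore those of subjects whose NAC has waned furthest, and the endpoint asks whether NAC is held to Days 45, 90 and 120.

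Two primary objectives depend on these tables. NAC is proposed in the Protocol synopsis as the bridge from animal efficacy to humans. Lot-to-lot variability has no formal analysis; instead, "the two lots within each of Cohorts 1 and 2 will be summarized and displayed separately to visually assess lot-to-lot variability". If BLQ frequency differs between lots, the rule could hide or create a visible difference.

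**Working it through.** The documents give no protective-NAC rate, MNA quantitation limit (LLOQ) or BLQ frequency, so there is no planned figure to reproduce. Every rate below is an assumption chosen to show the mechanism.

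**Inputs.** 75 subjects per dose-lot group (SAP Table 1), of whom 25 are fully tested and 50 sparsely tested (SAP 3.4). Assumed: LLOQ at or below target, Day 1 pre-dose sample BLQ, and all 75 subjects with PD results and in the PD population.

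**Scope of the rule.** SAP 8.3 also imputes 0.001 for zeros in geometric means and coefficients of variation. SAP 9.10.6 applies those statistics to NAC values at each visit as well as to AUC and Cmax. This indicates that the rule is meant to reach visit-level NAC data.

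**Who can drop out.** The SAP does not say whether the search for the first measurable value restarts at Dose 2, so there are three readings:

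| Reading | Day 45 | Day 90 | Day 120 |
|---|---|---|---|
| No restart | fully tested only | fully tested; sparse if measurable at Day 45 | fully tested; sparse if measurable at Day 45 or 90 |
| Restart after the Day 45 pre-dose sample | fully tested only | fully tested if measurable at Day 49; no sparse | fully tested if measurable at Day 49 or 90; sparse if measurable at Day 90 |
| Restart with the Day 45 pre-dose sample as first Dose 2 sample | none (BLQ is set to zero) | fully tested if measurable at Day 45 or 49; sparse if measurable at Day 45 | fully tested if measurable at Day 45, 49 or 90; sparse if measurable at Day 45 or 90 |

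Under the first two readings, the same Day 45 BLQ result is missing for a fully tested subject who was measurable earlier and a failure for a sparsely tested one.

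**Single-serotype rate.** With s successes, n subjects and b dropped BLQ failures, the rate moves from s/n to s/(n − b), which cannot be lower. From 60/75 = 80.0%:
- b = 4: 60/71 = 84.5%
- b = 8: 60/67 = 89.6%
- b = 15: 60/60 = 100%
- b = 0: no change

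**By visit, as upper bounds.** Keep 60/75 and suppose that all 15 failures are BLQ, spread evenly over the schedules (5 fully tested, 10 sparse), and that every fully tested failure had an earlier measurable value that counts.
- Day 45, first two readings: 60/(75 − 5) = 85.7%. Third reading: 80.0%.
- Days 90 and 120, with g the share of sparse failures that had an earlier measurable value that counts: 60/(75 − 5 − 10g). This gives 85.7% for g = 0, 92.3% for g = 0.5 and 100% for g = 1. At Day 90 under the second reading, g = 0 by construction.

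**Either-serotype rate.** The SAP does not say how to count a subject with one serotype set to missing. Take 60 successes, 20 of them late-BLQ on one serotype, and 15 failures. Rule A requires both serotypes non-missing. Rule B judges on whichever remains. Rule C sets the subject to missing if none is above target and at least one is missing.
- All failures measurable: A 40/55 = 72.7%; B and C 60/75 = 80.0%.
- Five failures late-BLQ on both serotypes, five on one, five on neither: A 40/45 = 88.9%; B 60/70 = 85.7%; C 60/65 = 92.3%.

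The rate can therefore fall, stay or rise.

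**Lot comparison, single serotype.** Suppose one lot is truly 60/75 (80.0%) with no BLQ, and the other 50/75 (66.7%) with 12 of its 25 failures late-BLQ. The second lot is shown as 50/63 = 79.4%. A true gap of 13.3 points appears as 0.6.

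**Group size.** Protocol 5.4.2 splits subjects 2:1 to give PD or PK specimens, which would leave 75 × 2/3 = 50 per lot, whereas Protocol 5.1 and SAP 3.4 collect PD samples from everyone. With 50, a true 40/50 (80.0%) becomes 40/45 (88.9%) if five failures drop out.

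**The case against.** The best opposing case is that the 8.3 rule is a profile convention. Its wording suits AUC and half-life, and the denominators say evaluable where they could have said measurable or non-missing. An assayed BLQ result can perfectly well be judged against a cut-off. This reading is possible but not written, and the 0.001 imputation for geometric means points the other way. Two programmers could follow the SAP and report different primary rates.

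Other parts of the objection stand and set limits on the point:
- A reader might infer that Day 45 is affected for everyone. It is not: the effect is mainly confined to the first 25 subjects per lot, and disappears if the Day 45 pre-dose sample opens the Dose 2 profile.
- A reader might infer that the rule always inflates the endpoint. That holds for a single serotype with the LLOQ at or below target. It does not hold in general for the either-serotype rate, which is the one defined in Table 2. If the LLOQ is above target, a dropped BLQ result is indeterminate and not a certain failure.
- Sparsely tested subjects have one sample after Dose 1 and two after Dose 2. Whether they meet the SAP 7.1.4 condition is not settled. If they do not, the contrast between testing schedules falls away.
- A reader might infer that the dropped results would be invisible. SAP 9.1 commits to listing all subject data, and 9.10.6 says "PD parameters and NAC values will be listed separately at the subject level". What is missing is only a statement that BLQ is shown as assayed, which 9.10.2 does give for laboratory qualifiers.

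**Conclusion.** The concern holds as an ambiguity with a real consequence. As written, the natural reading lets assayed BLQ results leave the denominator of a primary rate. It does not establish that the reported rates will be inflated. The size is unknown and may be zero, because neither the LLOQ nor the BLQ frequency is given. The move from 80.0% to 89.6% is an illustration that rests on eight dropped failures, a single serotype, an LLOQ at or below target and 75 analysed subjects per lot.

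The effect is clearest at Days 90 and 120. Cohort 4 at 2 to 8 hours should be little affected, since it requires a fall back to BLQ within hours of a measurable value. Protocol 11.1 and SAP 6 rule out formal hypothesis testing and no success threshold is set, so no test result changes. What is at stake is the accuracy of a primary estimate and of the by-eye lot comparison. It should be fixed before the final analysis.

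**What to change.** - **SAP 8.3:** leave the BLQ rule as it is for PD and PK parameters and for descriptive concentration summaries, which would otherwise have no rule. Add that it does not apply to the protective-NAC rates.
- **SAP 9.10.3, 9.10.4, 9.10.5 and 9.10.7:** define the denominator as PD-population subjects with a valid assayed NAC result at that time point, including BLQ. State the MNA LLOQ for each serotype.
- **Counting BLQ:** if the LLOQ is at or below target, count BLQ as not above target. Otherwise, show BLQ as a separate category within the denominator.
- **Either-serotype rate:** success if either assayed serotype is above target; failure if both assayed results are not above target; missing only if no assayed result is above target and at least one serotype was not assayed.
- **NAC listing:** show BLQ results as assayed.

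The cost is a few sentences and no new data. The reported rate may be less favourable.

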## Statistical Analysis Plan (SAP)

---

Additionally, NAC values will be summarized descriptively for each serotype separately at Baseline/Dosing [Visit 2 (Day 1)] pre-dose, Visit 3 (24 Hours), Visit 7 (Day 30), Visit 8 (Day 45), and Visit 9 (Day 90). Concentration-time profiles will be displayed graphically on linear and semi-log scales by serotype and active treatment group. One set of plots will include error bars (presented as SD) and one set will not include error bars.

The summary statistics used for all PD parameters and concentrations will include number of subjects (n), mean, SD, median, Q1, Q3, minimum, maximum, CV%, GM, the 95% CI of the GM, GCV%, and the 95% CI of GCV%.

The GM, 95% CI of GM, GCV%, and 95% CI of GCV% will be calculated using the following SAS® procedure:

```
proc ttest data=indata dist=lognormal;
  var x;
  ods select ConfLimits;
run;
```

, where `indata` is the data set with PD parameters and `x` is a parameter.

Additionally, PD parameters and NAC values will be listed separately at the subject level.

The PD population will be used for all pharmacodynamic tables, listings, and figures.

Immunogenicity (ADA) samples will be collected at Baseline/Dosing [Visit 2 (Day 1)] pre-dose, Visit 9 (Day 90), and Visit 10 (Day 120).

The frequency and percentage of subjects with a positive immunogenicity response will be summarized by mAb and time point across the active treatment arms. Results will be categorized as Detected, Not Detected, and NRR (No Recorded Result). Additionally, anti-drug antibody titers for the overall drug product will be summarized using continuous descriptive statistics [number of subjects (n), mean, SD, median, Q1, Q3, minimum, maximum, CV%, GM, 95% CI of the GM, GCV%, and the 95% CI of the GCV] by the aforementioned time points. Both the categorical and continuous ADA table summaries will include a subgroup analysis for only those subjects that have a negative immunogenicity response at baseline. Anti-drug antibody status and titer values will be listed by subject and time point.

The ITT population will be used for all immunogenicity summaries.

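### ADA titers reported as below the threshold T are analysed as T and pooled with measured titers, with no summary among ADA-positive samples; at low incidence the geometric mean and quartiles may not show titer magnitude

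*SAP*

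**What the plan says.** SAP 8.3 lists the exceptions to its no-imputation rule. For ADA: "Titer values presented as inequalities due to being below the detectable threshold will be reported as their numeric value without the inequality qualifier". Below-limit PK and PD results are handled differently: zero before the first measurable value, missing after it, and then "In the calculation of geometric means and coefficients of variation, 0.001 will be imputed for zero values".

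SAP 9.10.6 (Cohorts 1-2) says "anti-drug antibody titers will be summarized using continuous descriptive statistics" at each time point. The list includes mean, SD, median, quartiles, maximum, GM and geometric CV. SAP 9.10.9 (Cohort 4) says "anti-drug antibody titers for the overall drug product will be summarized using continuous descriptive statistics", with a similar list. Neither section limits the titer summary to ADA-positive samples. The one subgroup is this: "Both the categorical and continuous ADA table summaries will include a subgroup analysis for only those subjects that have a negative immunogenicity response at baseline". On the population: "The ITT population will be used for all immunogenicity summaries".

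Status is tabulated apart from titer. For Cohorts 1-2: "The frequency and percentage of subjects with a positive immunogenicity response will be summarized by time point across the active treatment arms". Cohort 4 has a corresponding detected / not detected table by antibody. Both sections list status and titer for each subject.

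**The concern.** Protocol 11.5.6 evaluates immunogenicity by two measures, ADA incidence and antibody titer. The titer table should therefore show something the incidence table does not: how strong the response is in those who have one. A table that gives T to every `<T` result and averages it with measured titers can lose that.

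The comparison by lot is where this would count. Evaluating lot-to-lot variability is a primary objective, and SAP 2.1 plans no formal analysis for it, only visual comparison of lots shown separately in the tables. Protocol 11.2 names immunogenicity parameters in the interim lot comparison (SAP 4.1 mentions only PK and PD). With no test planned, the descriptive tables are the whole analysis.

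**Working it through.** **Inputs.** The documents give no ADA incidence, threshold or titer distribution, so there is no figure of theirs to reproduce. Everything below is expressed in multiples of T and uses assumed ranges:
- share of samples with a titer above T: p = 5% to 80%;
- GM among positives: rT, with r = 4, 16 or 64;
- every other sample arrives as `<T` and is stored as T.

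**Geometric mean.** On the log scale, ln(GM/T) = (1 − p)·ln 1 + p·ln r, so GM = T·r^p.

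| p | r = 4 | r = 16 | r = 64 |
|---|---|---|---|
| 5% | 1.07T | 1.15T | 1.23T |
| 10% | 1.15T | 1.32T | 1.52T |
| 20% | 1.32T | 1.74T | 2.30T |
| 40% | 1.74T | 3.03T | 5.28T |
| 60% | 2.30T | 5.28T | 12.13T |
| 80% | 3.03T | 9.19T | 27.86T |

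The GM among positives is 4T, 16T or 64T in every row.

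**Quartiles and geometric CV.** These come from a simulated mixture (400,000 draws, lognormal positives with an assumed geometric SD of 3, floored at T).
- At p = 5%, 10% and 20%, Q1, median and Q3 all equal T for every r.
- At p = 40%, the median is T (probability 0.96 in a lot of 75), but Q3 is 2.8T, 11T or 45T.
- At p = 60%, the median is 1.4T, 5.5T or 22T.
- The geometric CV moves both ways. It is 40% against 131% among positives at p = 5%, r = 4, and about 1010% against 153% at p = 40%, r = 64.

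**Two lots side by side.**
- Lot 1, 10% positive at 16T: GM = 16^0.10·T = 1.32T.
- Lot 2, 20% positive at 4T: GM = 4^0.20·T = 1.32T.

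The GM, median, Q1 and Q3 agree, while the responders' titers differ by 16/4 = 4 times. The arithmetic means do differ: 0.9 + 0.1 × 16 = 2.5T against 0.8 + 0.2 × 4 = 1.6T. The mean is no cleaner a measure of magnitude, however, since 50% positive at 4T also gives 0.5 + 0.5 × 4 = 2.5T.

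**Does a negative sample carry `<T`?** The SAP does not say. Two features suggest it: 8.3 provides a rule for such records, and 9.10.6 and 9.10.9 repeat the titer table in baseline-negative subjects. If negatives carry `<T`, the baseline row of that table is T for everyone with zero spread. If they carry no titer, the row is empty, p among the titers is close to 100%, and the rule has almost no effect.

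**The case against.** The strongest reply is that the effect rests on an unstated data format. The rule covers only titers shown as inequalities, and Cohort 4 treats status (by antibody) and titer (for the overall product) as separate variables. A detected sample could also have a titer of `<T`. This stands, and the point is therefore conditional.

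A reader might infer that the titer tables describe the assay limit rather than the antibody response, or that a high-titer minority is hidden. The documents do not support either. The substitution does not touch the incidence table, the maximum reflects true positives, the arithmetic mean can be moved by them, and status and titer are listed per subject. The effect also fades as incidence rises. One reservation concerns the listings: SAP 9.10.2 keeps qualifiers in the laboratory listings, but nothing equivalent is said for ADA, so `<T` may be listed as T.

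It is also fair to say that ADA is a descriptive secondary endpoint, that no decision rule uses the GM titer, and that Protocol 11.5.6 does not ask for a restriction to positives. This limits the consequence. It does not supply the missing view of magnitude.

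**Conclusion.** The point holds conditionally. If negatives are reported as `<T` and incidence is low (up to about 20% in the scenarios), the median and quartiles equal T and the GM is 1.07T to 2.30T where responders average 4T to 64T. A lot or dose difference in titer magnitude need not show in those statistics. From about 50% incidence the median reflects positives too. All incidences, titer ratios and the geometric SD are assumptions.

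A reader might conclude that the 8.3 rule should be deleted and the all-subject table replaced by one in positives only. That does not follow. Deletion would leave a detected sample with a `<T` titer without a handling rule, and a positives-only table compares subsets defined after dosing. Substituting T/2 only moves the floor: at p = 10% the GM becomes 0.62T, 0.71T or 0.81T for r = 4, 16 or 64.

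**What to change.** Keep the all-subject titer table, and keep the 8.3 rule for any detected sample whose titer is `<T`. Then:
- in 8.3, name T and state what titer, if any, a negative sample carries;
- in 9.10.6 and 9.10.9, add a titer summary among ADA-positive samples by visit, lot and dose, with n positive / N tested, and the maximum post-dose titer per positive subject;
- show the number of values at the limit beside each all-subject GM and median;
- keep the `<` qualifier in the ADA listings.

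The cost is SAP wording, one filtered table and one added count. The positives-only rows may have small n. They are not a randomised comparison and must be read with the incidence table. If negatives turn out to carry no titer, the added table largely repeats the existing one and nothing is lost.
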